17.3 Secondary Outcome Measures

1) Secondary HIV outcomes variables:

- a. VACS Index. Change in VACS Index score at 24 weeks compared with randomization (continuous; laboratory assays and demographics).
- b. CD4 Count. Change in CD4 count at 24 weeks following treatment initiation compared with randomization (count; laboratory assay).

2) Engagement in HIV Care Variables:

- a. ART prescribed. Proportion of participants prescribed ART within 24 weeks following randomization (binary; medical record abstraction).
- b. ART Adherence. Proportion of participants taking 100% of prescribed ART doses in the past month at 24 weeks for those prescribed ART at any point during the 24 week trial (binary; self-reported medication adherence measure).
- c. Retention in HIV Care: Proportion of participants with at least 1 HIV primary care visit in the past 12 weeks, measured at week 24. Adherence to HIV clinic visits in the year after ART initiation predicts HIV disease progression and death [164] (binary; medical record abstraction).
- d. HIV Risk Behaviors. Past 30 day injection drug use, unprotected sex, multiple sexual partners as measured by the RAB at week 24 (binary; self-report).
- e. Quality of life. Past 30 day health-related quality of life as measured by EQ-5D at week 24.

3) ART Adherence Mediation Variables:

- a. Days of Opioid Use. Number of days of opioid use since baseline, measured by Timeline Followback at 24 weeks (count; self-report).
- b. Opioid Abstinence. Past 30 day opioid abstinence (by Addiction Severity Index (ASI)-lite self-report, Time-Line Follow-Back (TLFB) and urine drug screen (UDS) confirmation) in the final 30 days of the 24 week trial (binary; self-report + UDS).

17.4 Sample Size and Duration of Recruitment Phase

The CTN-0067 CHOICES scale-up trial will randomize 350 participants with opioid use disorder who are unsuppressed at baseline from no more than 8 sites over approximately 22 months for a power of 80%. Justification for this decision follows.

The trial will be powered as a non-inferiority trial since the overall goal of the research is to add to rather than to supplant the available effective opioid agonist treatment options currently available.

17.5 Substantive Justification for a Non-Inferiority Design.

A non-inferiority trial and the attendant choice of margin must be justified not just statistically, but also on substantive grounds. A non-inferiority trial design is justified when the active control is well-established and effective, and when a non-active control would be unethical, as in the case of treatments for HIV infection [165]. Both conditions are salient to the CTN-0067 CHOICES scale-up study in that opioid agonist therapy with buprenorphine or methadone is considered the standard of care for treatment of opioid dependence in HIV infected patients [104], and placebo treatments for either opioid use disorder or HIV infection are unethical.

Reporting of non-inferiority methods must include [165, 166]:

- Non-inferiority margin (delta)
- Sample size calculation must take into account the margin
- Both ITT and per-protocol analyses must be presented
- Confidence intervals for the results must be presented
- Justification of the margin

The first 4 points have been addressed in other parts of this statistical section. The following section describes the justification for the margin.

17.6 Justification of the Non-Inferiority Margin

Little data exist to inform justification of non-inferiority margins. Given that our primary outcome measure is viral suppression, we reviewed recent non-inferiority trials comparing two antiretroviral regimens with viral suppression as the outcome. Noninferiority margins in these trials ranged from 10% to 15% [114, 167-169], though no published justification is provided for these estimates.

The only study to estimate virologic suppression in HIV-infected participants receiving BUP/NX was the BHIVES collaborative. BHIVES was an observational study of HIV-infected participants with opioid use disorder receiving office-based BUP/NX from their HIV providers. Participants not already on ART baseline were offered ART regimens available in 2004-2007, which were less potent than currently available regimens. Among 64 participants who were not prescribed ART at baseline and who were prescribed BUP/NX for at least 3 quarters, 57.3% achieved HIV viral suppression by 6 months (a timeframe comparable to CHOICES 24-week outcome) [29]. More information about the choice of margin is given in the following section on Power results.

[figure not shown]
17.7 Rationale for Sample Size

Figure 4 shows the non-inferiority margin required for power of (0.8, 0.9) (using the lower tail of the two-sided 95% confidence interval) as a function of the sample size for the non-inferiority test of XR-NTX versus TAU at 4 months, as estimated from data “random-assignment-bootstrapped” from the (opioid + overlap) group who were unsuppressed at baseline in the pilot study (CTN-0055). There are only 9 participants in the bootstrap population: 7 in Core and 2 in UBC. The random-assignment bootstrap approach was used at 4 months as a conservative way to estimate power in the scale-up (see appendix). The margin is expressed in terms of the risk ratio (RR), that

is, $\Pr(\text{suppressed} \mid \text{XR-NTX}) / \Pr(\text{suppressed} \mid \text{TAU})^1$. A horizontal reference line in **Figure 4** marks $\text{RR} = 0.75$, and vertical reference lines mark the intersection of the horizontal line with the power curves for $(0.8, 0.9)$. The vertical lines intersect the N axis at sample sizes of about $(350, 480)$. For a given sample size, use of a margin at or below the one specified by the relevant curved line will grant power in excess of that depicted by the line. For example, an RR margin less than or equal to 0.75 will grant a power of at least 90% for total sample size (both arms together) of about 480 , and will grant a power of at least 80% for total sample size of 350 . We have chosen this last point upon which to base our sample size.

This particular example is calculated using the Rose et al. binary RMVL model. The fixed effects in the model are treatment, visit number (continuous), time by treatment interaction, baseline alcohol, and site (categorical). The data for each participant are assumed to have an exchangeable correlation structure. Missing data are assumed to be unsuppressed. Note that cases in which the model failed to converge or converged but SAS flagged the result as questionable have been dropped from this analysis. The number of analyzed iterations was $(9020, 9492, 9696, 9819, 9848, 9869, \text{ and } 9911)$ for $n = (200, 250, 300, 350, 400, 450, 500)$, respectively. With the assumptions above, a non-inferiority sample size calculation was performed using commercial software PASS and got very similar results.

17.7.1 Figure 4. Non-inferiority margins granting power = 0.8 and 0.9 as a function of sample size

Additional Comments Concerning Choice of RR margin

The reasoning in the non-inferiority margin calculation of a RR of 0.75 is as follows:

¹ As we define it here, RR might better be termed a “benefit ratio,” but we shall retain the common usage.

Recall from above that, in BHIVES, 57.3% achieved HIV viral suppression. Let us assume that, in the absence of any treatment for OUD, the suppression rate will be about 15%, so that the treatment effect of the active control in CHOICES is about 42%. It makes intuitive sense that the non-inferiority margin should be some fraction of this, and this general approach is discussed by the FDA in their Guidance for Industry on Non-inferiority Clinical Trials [170]. We have chosen 1/3 as the clinically reasonable fraction. That is, if XR-NTX preserves 2/3 or more of the effect of BUP/NX over placebo, we will consider XR/NTX to be non-inferior to BUP/NX. This implies a margin of 14%. With this margin, we are implicitly saying that, if the true suppression probability for BUP/NX is 57%, then we consider any true XR/NTX suppression probability greater than 43% to indicate that XR/NTX is not inferior to BUP/NX.

[figure not shown]
To turn this reasoning into a RR calculation, NTX is non-inferior if the observed risk ratio significantly exceeds $43/57=0.75$.

The RR we can be derived from the pilot study data. There are 9 in the opioid + overlap group who started out un suppressed. Their last non-missing suppression status is as follows:

	TAU	NTX
Suppressed	3	2
Un suppressed	2	2

The suppression rates from the CTN-0055 pilot study are $(\text{TAU}, \text{NTX}) = (60\%, 50\%)$. To call NTX non-inferior, NTX needs to preserve at least 14 percentage points of the TAU suppression rate, which means an NTX suppression rate of at least $60\%-14\% = 46\%$ is needed. This means a RR of at least $46/60 = 77\%$. This is not much different from the $43/57 = 75\%$ discussed above. Note that data paucity militates against a more precise calculation of pilot study RR.

17.7.2 Figure 5. Implications for probabilities of fixing RR = 0.75 versus fixing a probability difference of 0.14

[figure not shown]

How different are the implications for probabilities if one fixes an RR at 0.75 versus a probability difference of 0.14? **Figure 5** shows, $p(\text{suppressed} \mid \text{NTX})$ as a function of $p(\text{suppressed} \mid \text{TAU})$ for a risk ratio of 0.75 (red dashed line) and a probability difference of 0.14 (blue solid line), with a vertical reference line at $p(\text{suppressed} \mid \text{TAU})=0.57$, where the two lines intersect. In the neighborhood of $p(\text{suppressed} \mid \text{TAU}) = 0.57$ (from, say 0.4 to 0.8), differences appear to be less than 0.05.

17.8 Duration of Recruitment Period

An enrollment simulation based on CTN-0055 data was run using only times from the study population of interest (opioid + overlap, not suppressed at baseline). Use of the pilot data for estimating duration of recruitment period is limited by the fact that the CTN-0055 CHOICES pilot study sites were encouraged to enroll both participants with OUD and also those with AUD. Enrollment of both groups occurred faster than anticipated, but the opportunity cost of enrolling AUD participants may have limited the observed pace of enrollment of OUD participants. Additionally, no attempt was made in CTN-0055 to enroll only participants with unsuppressed HIV viral loads. Using the pilot study data for only participants with OUD and non-suppressed HIV viral loads, times to recruitment assuming a target sample size of 350, drawn from sites that match the experience of the CTN-0055 sites (one site like UBC and 9 like CORE), are depicted in **Figure 6**. The intersecting reference lines for a sample of size 350 show that simulation suggests a recruitment period of about 1324 days = 44 months. We anticipate that expanding CTN-0067 to include 6-8 sites with a higher prevalence of HIV viral non-suppression among patients with untreated opioid use disorder will allow recruitment of 2 to 3 participants per month per site, thus requiring 22 months to recruit 350 participants.

17.8.1 **Figure 6.** Simulated times to enrollment of 350 participants from 8 sites like CORE Center.

17.9 Analysis of secondary outcomes

Secondary outcomes will be analyzed as indicated in the italicized text describing each secondary endpoint.

1) Secondary HIV outcomes:

- a. **Change in VACS index** at week 24 compared with randomization (score based on lab measurements). T-test.
- b. **Change in CD4 count** at 24 weeks following randomization compared with randomization (count; laboratory measurement). T-test.

2) Engagement in HIV Care:

- a. **ART prescribed** Change in the proportion of study participants prescribed ART within 24 weeks following randomization, compared to baseline (binary; medical record abstraction). *Each individual can be scored either 0 (not prescribed ART) or 1 (prescribed ART) at both baseline and follow-up, after which his or her outcome score will be the follow-up score minus the baseline score. Outcome scores will be analyzed via rank-based methods such as Wilcoxon rank-sum tests. Covariates can be considered via the cumulative logit model.*
- b. **ART Adherence** Proportion of participants taking 100% of prescribed ART doses in the past month at 24 weeks for those prescribed ART at any point during the 24 week trial (proportion; self-reported medication adherence measure). *Chi-squared test comparing proportion to treatment assignment, for those prescribed ART.*
- c. **Retention in HIV Care** Number of HIV primary care visits at 24 weeks (count, chart abstraction). *Outcome scores will be analyzed via rank-based methods such as Wilcoxon rank-sum tests.*
- d. **HIV Risk Behaviors** Past 30 day injection drug use, unprotected sex, multiple sexual partners as measured by the RAB at week 24 (binary; self-report). *Chi-squared test comparing proportion to treatment assignment.*
- e. **Quality of life** Past 30 day health-related quality of life as measured by EQ-5D at week 24. *Change from baseline in mean EQ5D score assessed by treatment group using paired t-test, or analysis of change via ordinary least squares.*

[figure not shown]
3) ART Adherence Mediation Variables and Mediation Analysis:

- a. **Days of Opioid Use** Number of days of opioid use between baseline and 24 weeks, measured by TLFB (count; self-report), will be used to compare opioid use by treatment group. Confirmatory analysis will assess opioid use by the number of days of opioid use in the last 30 days of the study (by ASI-lite; count; self-report) and the number of monthly urine drug screen (UDS) negative for opioids between baseline and 24 weeks (count; laboratory data). *Analyzed using rank-based methods such as Wilcoxon rank-sum tests.*
- b. **Opioid Abstinence** Past 30 day opioid abstinence (by Addiction Severity Index (ASI)-lite self-report, Time-Line Follow-Back (TLFB) and urine drug screen (UDS) confirmation) in the final 30 days of the 24 week trial (binary; self-report + UDS).

Analyzed via rank-based methods such as Wilcoxon rank-sum tests. Covariates can be considered via the cumulative logit model.

Mediation Analysis

Mediation will be tested using structural equation modeling with Mplus 7.3. These models estimate the effect of the intervention on the potential mediator (path a, e.g., the effect of intervention on *substance use*) and the effect of the mediator on the outcome or next proximal intermediate outcome (path b, e.g., the effect of *substance use* on *HIV medication adherence*). Longer mediation pathways can also be tested (e.g., a^*b^*c), and therefore the entire mediational path depicted in section 1.2.1 can be assessed in this framework. There is significant mediation if the product of these two paths (a^*b) is greater than zero (or the product of more pathways in a longer mediational chain). Statistical significance will be assessed using bias-corrected bootstrap confidence intervals on the product terms [171]. This test is by far the most powerful test of mediation [172] and can test multiple mediating pathways within a single structural model. Using the tables in Fritz and MacKinnon [171], we should have over 80% power for mediation when the standardized path coefficients (a and b) are .164, which corresponds to approximately 2.7% shared variance between the outcome and predictor variable (e.g., treatment and substance for the a-path in the example given above.) We will also examine whether there are differences in strength of mediational pathways across the opioid and alcohol disorder subgroups.

Qualitative Analysis of Implementation Data The qualitative team creates a coding scheme, practices coding, and revises in an iterative group process. Each transcript is coded and check-coding is completed with 20% of transcripts to ensure inter-coder reliability. The analysis uses a deductive approach to focus on themes related to select CFIR inner and outer setting, provider characteristics, and implementation characteristic domains. Iterative analyses assess convergence of CFIR patient, provider and organizational dimensions on study measures as well as the context of the policy subsystems, cross-system interactions, and resource allocation. A five phase strategy guides the analysis: describe themes, organize and structure data, connect codes and themes, corroborate and triangulate, and condense and summarize findings [173]. Site structural data will be triangulated with staff and patient qualitative interviews to integrate an environmental perspective.

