9.1.9 Randomization

The timing of randomization will follow shortly after baseline assessments and final confirmation of eligibility. Participants will be encouraged to initiate treatment within 28 days of randomization. If a participant is unable to initiate treatment within 28 days, he or she may initiate XR-NTX study drug at any time until week 20 and may initiate TAU at any time during the trial. Initiation of assigned treatment will be tracked.

Participants will be randomized in a 1:1 fashion to either office-based XR-NTX or TAU using a permuted block design with randomly-sized blocks. Randomization will be stratified only by site. Participants who meet DSM-5 criteria for both opioid and alcohol use disorder (16% of CTN-0055 CHOICES pilot study participants) will be included, in addition to participants with OUD, alone.

Concomitant alcohol use disorder will be considered as a potential covariate [31], [127, 128]. Participants need not be abstinent from opioids at the time of randomization.

The randomization procedure will be conducted in a centralized process through the Data and Statistics Center (DSC). Specifically, randomization schedules will be created by the study statistician for each site. The randomization schedules will be of a randomized-block nature to ensure relative equality of assignment across condition across the recruitment period and to prevent the potential for study staff guessing the next assignment, which is heightened when a fixed block-size is used. After the baseline assessment is successfully completed, a designated site study staff member will perform the randomization. Randomization for each participant is done over the internet using the Enrollment Module in Advantage eClinical.

The DSC statistician will review the randomization data on a regular basis to ensure that the scheme is being implemented according to plan. If a participant drops out of the study at any point after randomization, the randomization slot will not be re-allocated to a new participant due to the intent-to-treat nature of the study.

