Concise Health Risk Tracking – Self Report			X		X	X	X	X	X	X	X	X		
Concise Health Risk Tracking – Clinician Rated														X
DSM-5 Substance Use Disorders		X												
Urine Drug Screen		X			X*	X*	X	X	X	X	X	X	X	
HIV Care Utilization			X										X	X
Buprenorphine and Methadone Chart Abstraction							X	X	X	X	X	X	X	
Quality of Life, from PhenX			X											
Quality of Life, from EQ-5D			X									X	X	

Assessment/Activity	Pre-Screening	Screening	Baseline	Randomization ^{^A}	Treatment Initiation	Safety Visit	Week 4	Week 8	Week 12	Week 16	Week 20	Week 24	End of Study (#Week 24)	As Needed
Risk Assessment Battery			X				X	X	X	X	X	X	X	
Tobacco Use History and Substance Use History, from PhenX			X									X	X	
Timeline Follow Back			X		X		X	X	X	X	X	X	X	
Treatment Plan				X			X	X	X	X	X	X	X	
Treatment Initiation***													X	X
XR-NTX Non-Initiation*														X
Treatment Satisfaction Survey													X	X
Treatment Services Review			X		X		X	X	X	X	X	X	X	
VACS Index				X									X	X
Visual Analog Scale			X				X	X	X	X	X	X	X	
PHQ-9 Depression Symptoms			X						X			X	X	
Suicidal Risk														X
Criminal Justice			X						X			X	X	
Participant Treatment Preference			X											

* Only for participants randomized to the XR-NTX arm.

**At randomization, HCV PCR confirmation is required when HCV ab is positive. At 24 weeks, collect HCV ab if participant tested HCV ab negative at randomization or if HCV ab result was not obtained at randomization. At 24 weeks, collect HCV PCR confirmation if: HCV antibody is positive at randomization, but HCV PCR was not obtained at randomization or HCV antibody was negative at randomization, but HCV antibody is positive at Week 24.

*** Only for participants randomized to TAU arm.

[‡] Height and weight only for BMI calculations.

⁺⁺ Not captured in eClinical.

[^]Urine pregnancy test required for XR-NTX group only; remainder of Pregnancy and Birth Control Assessment required for all participants.

^{^A}Assessments performed at randomization correspond with Week 0 requirements in the eClinical system.

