11.4 VACS Index

The VACS Index is a validated biomarker score that reflects overall health and is a potent predictor of mortality in HIV-infected patients [147, 148]. The VACS Index is calculated by summing scores for age, CD4 count, HIV-1 RNA, hemoglobin, liver fibrosis (FIB-4), renal function (eGFR), and HCV status (**Table 11.1**) [148, 149]. It is responsive to abstinence among HIV-infected patients receiving opioid agonist treatment even when they enter such treatment with an undetectable HIV viral load [150]. A clinically meaningful difference is 5 points as it relates to a 20% change in 5-year mortality risk [147-149]. It will be assessed at randomization and week 24, or the end of study visit, if not week 24.

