17.9.1 Additional Statistical Tests of the Secondary Outcomes

In addition to the methods described after each secondary outcome, statistical modeling will be done using generalized estimating equations (GEEs) models as employed by Liang and Zeger [174] to allow covariate adjustment in factors such as concomitant alcohol use disorder and severity of opioid and alcohol use disorder. Those secondary outcomes that are binary will be tested with a binomial distribution and logit link as implemented in SAS; whereas those secondary outcomes that involve either continuous or ordinal variables will utilize the appropriate distribution and link function. Note that the exact method of analysis will depend on the realized distribution of the particular outcome in this trial. For example, an expected count data variable may need to be modeled using a zero-inflated Poisson regression rather than a standard Poisson regression if there are too many zero observations to fit the standard Poisson. If there is over-dispersion, a

negative binomial (or zero-inflated negative binomial) regression may be appropriate. For these secondary analyses, the overall Type I error will not be controlled.

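### Change in VACS Index and CD4 is tested by an unadjusted t-test; naming the baseline value and site as covariates would recover precision without new data

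*Combined protocol and SAP*

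**What the plan says.** Section 17.9 gives a method beside each secondary outcome. Item 1a, change in VACS Index, reads "at week 24 compared with randomization (score based on lab measurements). T-test". Item 1b, change in CD4, reads "at 24 weeks following randomization compared with randomization (count; laboratory measurement). T-test". Nothing further is specified for either. Both are read here as two-sample comparisons of the arms.

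Section 9.1.9 states "Participants will be randomized in a 1:1 fashion to either office-based XR-NTX or TAU", in permuted blocks, and "Randomization will be stratified only by site". The primary model in Section 17.2 carries site as a fixed effect.

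Section 17.9.1 adds GEE models on top of the named tests, "to allow covariate adjustment in factors such as concomitant alcohol use disorder and severity of opioid and alcohol use disorder". It leaves the exact method to depend on the realized distribution of each outcome. It also says "For these secondary analyses, the overall Type I error will not be controlled".

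**The concern.** Both biomarkers are measured at randomization (or taken from recent records) and at week 24, so each participant's baseline value is in hand. A change score uses it with a fixed coefficient of one. Regression estimates the coefficient, and in large samples it is never less precise. Blocking on site and then leaving site out of the test also yields a standard error that is too wide whenever outcomes differ between sites.

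Section 17.9.1 permits adjustment but does not settle it. The baseline value and site are not among the factors it mentions, and nothing ranks the GEE model against the t-test. A reader of the results could therefore meet two analyses of the same outcome without knowing which was meant to lead. At stake are the width of the confidence intervals and the chance of detecting a real difference on the two HIV biomarker outcomes.

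**Working it through.** The documents give no SD, correlation, power or sample size for VACS or CD4, so there is no stated figure to reproduce. What follows is relative efficiency over an assumed range.

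**Inputs.** From the documents: 175 per arm (Section 17.1), a 5-point clinically meaningful VACS difference (Section 11.4), stratification by site (Section 9.1.9). Assumed: baseline to week-24 correlation r of 0.5 to 0.9; VACS SD of 20 or 25; two-sided 5% tests; site share of variance of 1% to 10%.

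**Baseline adjustment, equal SDs s.** Var(change) = 2s²(1−r). Var(adjusted) = s²(1−r²). The ratio is (1+r)/2. The SE reduction is 1 − √ratio, and the number of adjusted participants equivalent to 350 on the change score is 350 × ratio.

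| r | Variance ratio | SE reduction | Adjusted N equivalent to 350 |
|---|---|---|---|
| 0.5 | 0.75 | 13.4% | 262 |
| 0.7 | 0.85 | 7.8% | 297 |
| 0.8 | 0.90 | 5.1% | 315 |
| 0.9 | 0.95 | 2.5% | 332 |

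**Unequal SDs, s0 at baseline and s1 at week 24.** Var(change) − Var(adjusted) = s0² + s1² − 2r·s0·s1 − s1²(1−r²) = (s0 − r·s1)². This is never negative, and it is zero when s1/s0 = 1/r. Example: s0 = 1, s1 = 1.25, r = 0.8 gives Var(change) = 1 + 1.5625 − 2 = 0.5625 and Var(adjusted) = 1.5625 × 0.36 = 0.5625, so there is no gain.

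**Power for a 5-point VACS difference, 175 per arm, equal SDs.** At SD 20 and r = 0.5 the change SD is 20√(2×0.5) = 20 and its SE is 20√(2/175) = 2.14. The adjusted SD is 20√0.75 = 17.3, with SE 1.85.

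| SD | r | Change t-test | Baseline-adjusted |
|---|---|---|---|
| 20 | 0.5 | 64.7% | 77.0% |
| 20 | 0.7 | 85.5% | 90.6% |
| 20 | 0.8 | 95.9% | 97.4% |
| 25 | 0.5 | 46.4% | 57.9% |
| 25 | 0.7 | 67.6% | 74.5% |
| 25 | 0.8 | 84.1% | 87.7% |

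**Site.** If site explains a share k of the residual variance, including it lowers the reported SE by 1 − √(1−k): 0.5%, 2.5% and 5.1% at k = 1%, 5% and 10%. With arms balanced within site, a t-test that ignores site has a true two-sided level set by 1.96/√(1−k): 2.01 (about 4.4%) at k = 5% and 2.07 (about 3.9%) at k = 10%. A simulation of 350 participants at 7 sites with r = 0.5 and 3000 repetitions gave 4.5% and 3.9%. At SD 20, r = 0.5 and k = 5%, the same simulation gave power of 66.6% for the t-test and 79.6% for the model with baseline and site.

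**VACS age points, only if age is updated at week 24.** Table 1 in Section 11.5 scores age 0, 12 and 27, so the steps are +12 at 50 and +15 at 65. With the pilot mean age of 46 (Section 4.3) and an assumed SD of 10, about 1.71% turn 50 and 0.32% turn 65 within 24 weeks.
- Mean shift: 0.0171×12 + 0.0032×15 = 0.25 points.
- Variance: 0.0171×144 + 0.0032×225 − 0.25² = 3.1.

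Over mean ages of 46 to 50 and age SDs of 8 to 12, removing these points lowers the SE by about 0.4% if the VACS-change SD is 20, and by up to about 2% if it is 10.

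**The case against.** The case for leaving the plan alone is fair. The t-test on change is valid and already uses the baseline by subtracting it. These are secondary outcomes with no power target and no multiplicity control. Section 17.9.1 already plans covariate-adjusted models, and its list of factors is illustrative, so baseline and site could be included. The size of the gain depends on a correlation that the documents do not give: at r = 0.9 it is small, and with a larger week-24 SD it can vanish.

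All of this limits the size of the point, and none of it reverses the direction. An open list of covariates permits adjustment without pre-specifying it, and the ranking of the two analyses is still missing.

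A reader might infer three stronger claims that the documents do not support.

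- **The plan ignores baseline, or the comparison is biased.** It does neither. The loss is precision, plus slight conservatism from omitting site.
- **VACS change contains birthday points.** Section 11.4 says "The VACS Index is calculated by summing scores for age, CD4 count, HIV-1 RNA, hemoglobin" and further components, so age is in the score. No section says that the age band is recomputed at week 24. The demographics form is scheduled only at screening; date of birth is collected, so recomputation is possible but not established. If it is done, the shift is expected equally in both arms.
- **The hepatitis C component can only rise and has nothing to do with treatment.** The footnote in Section 10.1 says "At 24 weeks, collect HCV ab if participant tested HCV ab negative at randomization", but it also orders week-24 PCR where antibody was positive at randomization and no PCR was obtained. Such a participant's score could fall. Table 1 does not say whether antibody or PCR defines the component. New infection may follow injecting, which is itself among the secondary outcomes, so freezing the component could remove a real effect.

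**Conclusion.** The point stands as an efficiency improvement of minor weight. Items 1a and 1b rely on an unadjusted t-test, and Section 17.9.1 neither names the baseline biomarker and site nor says which analysis leads.

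Under equal SDs, baseline adjustment cuts the SE by 2.5% to 13.4% as the assumed r falls from 0.9 to 0.5. The gain shrinks to nothing as the week-24 SD approaches the baseline SD divided by r. Site adds a further 0.5% to 5.1% if it explains 1% to 10% of the residual variance, and including it restores the nominal level. The VACS age points matter only if age is updated, and then by about 0.4% to 2% of the SE with no expected bias. The primary outcome is not affected.

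**What to change.** In Section 17.9 items 1a and 1b, make the main analysis a linear model of the week-24 value on treatment, the baseline value of the same biomarker and site. Modelling change instead gives the same treatment estimate once baseline is a covariate. Report the adjusted difference with its 95% CI and keep the t-test as a check. State in Section 17.9.1 that its GEE models are supportive for these two outcomes.

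Optionally, add one sentence saying that the VACS age-band points are held at the age at randomization, or report that version as a sensitivity analysis. Label it clearly, because the 5-point threshold is stated for the index as the protocol defines it. For the same reason, leave FIB-4, eGFR and hepatitis C scored as defined.

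The cost is a few lines of text and minor programming. No new data are needed, and with no more than 8 sites the site term uses at most 7 degrees of freedom out of 350 participants.
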